### **Durvalumab Adverse Events of Special Interest**

Adverse Events of Special Interest (AESI) for durvalumab include but are not limited to events with a potential inflammatory or immune-mediated mechanism and which may require more frequent monitoring and/or interventions such as steroids, immunosuppressants and/or hormone replacement therapy. These AESIs are being closely monitored in clinical studies with durvalumab monotherapy and combination therapy. An immune-related adverse event (irAE) is defined as an adverse event that is associated with drug exposure and is consistent with an immune-mediated mechanism of action and where there is no clear alternate aetiology. Serologic, immunologic, and histologic (biopsy) data, as appropriate, should be used to support an irAE diagnosis. Appropriate efforts should be made to rule out neoplastic, infectious, metabolic, toxin, or other etiologic causes of the irAE.

If the Investigator has any questions in regards to an AE being an irAE, the Investigator should promptly contact the Study Physician.

AESIs based on observed safety events using durvalumab monotherapy and/or class effects for inhibitors of PD-L1 or PD-1 include:

- Colitis
- Pneumonitis
- ALT/AST increases / hepatitis / hepatotoxicity

- Neuropathy / neuromuscular toxicity (i.e., events of encephalitis, peripheral motor and sensory neuropathies, Guillain-Barré, and myasthenia gravis)
- Endocrinopathy (i.e., events of hypophysitis, adrenal insufficiency, and hyper- and hypothyroidism)
- Type 1 diabetes mellitus
- Rash/ dermatitis
- Nephritis
- Pancreatitis (or labs suggestive of pancreatitis - increased serum lipase, increased serum amylase)

Further information on these risks (e.g., presenting symptoms) can be found in the current version of the [Investigator's Brochure V10.0-Durvalumab](#).

#### **1.3.4 Durvalumab Human Pharmacokinetics**

As of 09 Feb2015, PK data were available for 378 subjects in the dose-escalation and dose-expansion phases of Study CD-ON-durvalumab-1108 following treatment with durvalumab 0.1 to 10 mg/kg every 2 weeks (Q2W) or 15 mg/kg every 3 weeks (Q3W). The maximum observed concentration ( $C_{max}$ ) increased in an approximately dose-proportional manner over the dose range of 0.1 to 15 mg/kg. The area under the concentration-time curve from 0 to 14 days ( $AUC_{0-14}$ ) increased in a greater than dose-proportional manner over the dose range of 0.1 to 3 mg/kg and increased dose-proportionally at  $\geq 3$  mg/kg. These results suggest durvalumab exhibits nonlinear PK likely due to saturable target-mediated CL at doses  $< 3$  mg/kg and approaches linearity at doses  $\geq 3$  mg/kg. Near complete target saturation (soluble programmed cell death ligand 1 [sPD-L1] and membrane bound) is expected with durvalumab  $\geq 3$  mg/kg Q2W. Exposures after multiple doses showed accumulation consistent with PK parameters estimated from the first dose. In addition, PK simulations indicate that following durvalumab 10 mg/kg Q2W dosing,  $> 90\%$  of subjects are expected to maintain PK exposure  $\geq 40$   $\mu\text{g/mL}$  throughout the dosing interval.

A population PK model was developed for durvalumab using monotherapy data from a Phase 1 study (Study 1108; N=292; doses= 0.1 to 10 mg/kg Q2W or 15 mg/kg Q3W; solid tumors). Population PK analysis indicated only minor impact of body weight (WT) on PK of durvalumab (coefficient of  $\leq 0.5$ ). The impact of body WT-based (10 mg/kg Q2W) and fixed dosing (750 mg Q2W) of durvalumab was evaluated by comparing predicted steady state PK concentrations (5th, median and 95th percentiles) using the population PK model. A fixed dose of 750 mg was selected to approximate 10 mg/kg (based on median body WT of  $\sim 75$  kg). A total of 1000 patients were simulated using body WT distribution of 40–120 kg. Simulation results demonstrate that body WT-based

and fixed dosing regimens yield similar median steady state PK concentrations with slightly less overall between-subject variability with fixed dosing regimen. Based on average body WT of 75 kg, a fixed dose of 1500 mg Q4W durvalumab (equivalent to 20 mg/kg Q4W) is included in the current study.

As of 09 Feb2015, a total of 388 subjects provided samples for ADA analysis. Only 8 of 388 subjects (1 subject each in 0.1, 1, 3, and 15 mg/kg cohorts, and 4 subjects in 10 mg/kg cohort) were ADA positive with an impact on PK/pharmacodynamics in 1 subject in the 3 mg/kg cohort.

### **1.3.5 Durvalumab Monotherapy Clinical Activity in Solid Tumor Diseases**

In Study CD-ON-durvalumab-1108, 456 of 694 subjects treated with durvalumab 10 mg/kg Q2W were evaluable for response (defined as having  $\geq 24$  weeks follow-up, measurable disease at baseline, and  $\geq 1$  follow-up scan, or discontinued due to disease progression or death without any follow-up scan). In PD-L1 unselected patients, the objective response rate (ORR), based on investigator assessment per Response Evaluation Criteria in Solid Tumors (RECIST) v1.1, ranged from 0% in uveal melanoma (n = 23) to 20.0% in bladder cancer (n = 15), and disease control rate at 24 weeks (DCR-24w) ranged from 4.2% in triple-negative breast cancer (TNBC; n = 24) to 39.1% in advanced cutaneous melanoma (n = 23). PD-L1 status was known for 383 of the 456 response evaluable subjects. Across the PD-L1-positive tumors, ORR was highest for bladder cancer, advanced cutaneous melanoma, hepatocellular carcinoma (HCC; n = 3 each, 33.3% each), NSCLC (n = 86, 26.7%), and squamous cell carcinoma of the head and neck (SCCHN; n = 22, 18.2%). In the PD-L1-positive subset, DCR-24w was highest in advanced cutaneous melanoma (n = 3, 66.7%), NSCLC (n = 86, 36.0%), HCC and bladder cancer (n = 3 each, 33.3% each), and SCCHN (n = 22, 18.2%).

## **1.4 Expectations for Combination of Mocetinostat and Durvalumab**

### **Potential for Drug-Drug Interactions**

Treatment with mocetinostat in combination with durvalumab is unlikely to result in clinically relevant metabolism or elimination-based drug-drug interactions (DDI). Durvalumab is a mAb and is intravenously administered, whereas mocetinostat is a small molecule therapeutic administered orally; no absorption interaction is expected.

The fractional binding of MGCD0103 to human plasma was measured via equilibrium dialysis. At concentrations of 0.5, 1 and 10  $\mu\text{M}$ , MGCD0103 showed binding of 95.1%, 97.5%, and 95.2%, respectively. MEDI4736 is a mAb and only binds specifically to IgG1 $\kappa$ , therefore, no risk of distribution interaction is expected.

Reaction phenotyping results indicated that MGCD0103 was metabolized by CYP2E1 and CYP3A and possibly CYP2C8 and 2C19. No studies on the metabolism of MEDI4736 have been performed *in vitro* or in humans. Like most therapeutic proteins, MEDI4736 is not expected to be metabolized by liver cytochrome P450 (CYP) or other drug metabolizing enzymes and is unlikely to have an effect on CYPs or other metabolizing enzymes in terms of inhibition or induction.

### **Evaluation of Potential for Increased Toxicities with Combination Use of Mocetinostat and Durvalumab**

PD-L1 is part of a complex system of receptors and ligands that are involved in controlling T-cell activation. PD-L1 acts at multiple sites in the body to help regulate normal immune tolerance and is utilized by tumors to help evade detection and elimination by the host immune system tumor response. Durvalumab (MEDI4736) is a mAb that inhibits binding of PD-L1 to PD-1 and CD80.

Mocetinostat (MGCD0103) is a small molecule inhibitor of Class I and IV HDACs. HDACs are involved in cellular processes such as cell cycle progression and differentiation and have been implicated in the epigenetic regulation of innate and adaptive immunity. Evidence supports the proposal that spectrum-selective inhibitors of Class I HDACs can reverse immune evasion and elicit antitumor efficacy through induction of PD-L1 expression; enhanced tumor antigenicity via induction of TAAs and MHC Class I and Class II molecules; activation and cross-presentation of tumor antigens by APCs; enhanced function of T effector cells; and decreased function of immunosuppressive cell subsets including Treg cells and MDSCs.

When viewed together, the safety profiles of mocetinostat and durvalumab are largely non-overlapping. Frequently observed AEs common to treatment with single agent durvalumab and mocetinostat are non-specific and typical of cancer treatment regimens, including fatigue, anorexia, nausea, vomiting, and diarrhea. Potential exists for these AEs to be observed with increased severity or frequency during use of the combined agents. Management of these effects in patients receiving cancer therapy is well precedented.

More importantly, immune-related AEs of Special Interest based on observed safety events using durvalumab monotherapy and/or class effects for inhibitors of PD-L1 or PD-1 include colitis, pneumonitis, ALT/AST increases / hepatitis / hepatotoxicity, neuropathy / neuromuscular toxicity, endocrinopathy, dermatitis, nephritis and pancreatitis. While Class I HDAC inhibitors may have immunostimulatory effects, autoimmune adverse effects have not been reported in mocetinostat clinical trials or as a class effect. The potential for mocetinostat to exacerbate or promote these adverse events when administered in combination with durvalumab should be borne in mind.

One clinically relevant overlap in toxicity may arise between the immune-related colitis attributed to durvalumab and the non-specific, most often mild to moderate diarrhea observed with both durvalumab and mocetinostat. Immune-related colitis has been reported in approximately 0.8% of patients treated with durvalumab, with a time to onset ranging from 43 to 138 days after the first dose. Diarrhea of uncertain etiology has been reported in approximately half of patients treated with mocetinostat, most often with a time to onset within 30 days of first mocetinostat dose. Low grade diarrhea is less common with durvalumab, occurring in fewer than 8% of patients treated at 10 mg/kg Q2W in Study CD-ON-durvalumab-1108. The time to onset may be helpful in distinguishing diarrhea that may be attributed to autoimmune effects versus non-specific toxicity.

Two AEs observed in previous clinical trials of mocetinostat for which causality and mechanism are unclear are cystitis and pericardial effusion. The potential for an immune-based mechanism exists, therefore increased risk may be associated with the combination of mocetinostat with durvalumab.

## **1.5 Study Rationale**

Advanced tumors evade host immune responses by down regulation of major histocompatibility complex (MHC) molecules and tumor antigens and by creating an immune suppressive microenvironment around the tumor. Histone deacetylases (HDACs) have been implicated in the epigenetic regulation of innate and adaptive immunity. Increasing evidence supports the proposal that spectrum-selective inhibitors of class I HDACs can reverse immune evasion and elicit antitumor host response through immunostimulatory mechanisms. The immunomodulatory properties of class I HDAC inhibitors are reported to be mediated through multiple mechanisms including: 1) induction of programmed cell death ligand 1 (PD-L1) expression on the tumor cell surface, 2) induction of tumor associated antigens (TAAs) and MHC Class I and Class II molecules on tumor cells, 3) induction of immunogenic cell death via activation and cross-presentation of tumor antigens by antigen presenting cells (APCs), 4) enhanced function of T effector cells, and 5) decreased function of immunosuppressive cell subsets including T regulatory (Treg) cells and myeloid-derived suppressor cells (MDSCs). In addition, HDAC inhibitors are associated with anticancer effects through inhibiting cell cycle progression and inducing apoptosis in tumor. The combination of a class I HDAC inhibitor with an anticancer immunotherapy has the potential to enhance activity over that observed with either agent alone.

Mocetinostat is a spectrum-selective Class I/IV HDAC inhibitor specifically targeting HDACs 1, 2, 3 and 11. Class I and IV HDACs are of particular interest from an immunostimulatory and immune priming perspective.

Durvalumab is a human monoclonal antibody (MAb) that inhibits binding of PD-L1 to programmed cell death 1 (PD-1) and CD80 expressed on host immune effector cells, preventing immune suppression signaling. Durvalumab is being developed as a potential anticancer therapy for patients with advanced solid tumors or hematological malignancies.

The percent of tumor cells expressing PD-L1 is predictive for responsiveness to treatment with durvalumab (Rebelatto-2015). The recommended threshold for positivity is  $\geq 25\%$  of tumor cells demonstrating membrane staining for PD-L1 at any intensity. Among patients with NSCLC, the ORR for cases positive for PD-L1 was 27% (23 of 84; 95% Confidence Interval [CI] 18.2-38.2%) as compared to 5% (5 of 92; 95% CI 1.8-12.2%) for cases negative for PD-L1 expression (Rizvi-2015). Subset analysis by histological classification shows the following disease response rates:

Histology	All Patients	PD-L1 +	PD-L1 -
Squamous	18/88 (21%)	14/43 (33%)	3/37 (8%)
Non-squamous	14/122 (13%)	9/41 (22%)	2/55 (4%)

In this study, the treatment regimen will begin with a 7-Day Lead-In Period of mocetinostat followed by start of the combination regimen of mocetinostat and durvalumab. The Recommended Phase 2 Dose (RP2D) of mocetinostat will be established in the Phase 1 dose escalation segment, followed by evaluation of the clinical activity of the combination regimen in patients having NSCLC.

## **2 STUDY OBJECTIVES**

### **2.1 Objectives**

#### **2.1.1 Primary Objectives**

- To determine the RP2D of mocetinostat administered in combination with full dose durvalumab.
- To evaluate the clinical activity of mocetinostat in combination with durvalumab in cohorts of patients with NSCLC having differing tumor expression of PD-L1 or prior tumor responsiveness to treatment with checkpoint inhibitors.

#### **2.1.2 Secondary Objectives**

- To evaluate the safety and tolerability of mocetinostat in combination with durvalumab in the selected population.
- To evaluate secondary efficacy endpoints with mocetinostat in combination with durvalumab treatment in the selected population.
- To evaluate mocetinostat and durvalumab PK.
- To evaluate the incidence of ADA to durvalumab.
- To evaluate the effect of mocetinostat during the Lead-In Period on tumor cell PD-L1 expression.

[REDACTED]

[REDACTED]

[REDACTED]

[REDACTED]

### **2.2 Endpoints**

#### **2.2.1 Primary Endpoints**

- Incidence of DLTs occurring during the first 28-day cycle of combination treatment.
- ORR as defined by RECIST 1.1.

### 3 STUDY DESIGN

Study 0103-020 is an open-label Phase 1/2 evaluation of mocetinostat in combination with durvalumab. The Phase 1 segment will define the RP2D of mocetinostat to be used in combination with the full dose regimen of durvalumab; eligible patients will have an advanced solid tumor disease that is not amendable to curative treatment. The Phase 2 segment will evaluate the clinical activity of mocetinostat in combination with durvalumab, as assessed by ORR in accordance with RECIST 1.1., in patients with locally advanced, unresectable or metastatic NSCLC who have previously received at least one platinum-containing doublet chemotherapy regimen for advanced disease. Patients who have previously received treatment with checkpoint inhibitors may be enrolled in the Phase 1 assessment and will be enrolled into dedicated cohorts in the Phase 2 assessment. Secondary objectives include secondary efficacy endpoints, PK, incidence of ADA and change in tumor PD-L1 expression.

The Schedule of Assessments to be performed in the study is presented in [Table 1](#). Triplicate ECG assessments, PK, and ADA collection time points are presented in [Table 2](#).

The treatment regimen to be evaluated in this study includes a 7-Day Lead-in Period of mocetinostat single agent administered TIW (e.g., Monday, Wednesday and Friday) followed by administration of the combination regimen with durvalumab. The RP2D dose of mocetinostat will be established in successive dose escalation cohorts in the Phase 1 study and utilized in the Phase 2 study. The dose and regimen of durvalumab to be used throughout the study is 1500 mg on Day 1 of each 28-day cycle (i.e., Q4W). Guidelines for adverse event management and associated treatment modifications of each agent are provided in [Section 5](#).

#### 3.1 Phase 1 Study

The dose escalation phase of the study will employ the mTPI method will be employed in decision making concerning mocetinostat dose escalation ([Appendix 2](#)).

The mocetinostat dose levels planned for evaluation include 50, 70, and 90 mg TIW, depending on safety observations. In addition, if necessary, dose de-escalation of mocetinostat to 40 mg TIW may be undertaken.

##### 3.1.1 Definition of Dose Limiting Toxicity

The National Cancer Institute Common Toxicity Criteria for Adverse Events (NCI CTCAE) version 4.03 will be used throughout this study. The definition of DLT includes any of the following events considered to be causally related to treatment with mocetinostat in combination with durvalumab:

- Any Grade 4 immune-related Adverse Event (irAE is defined in [Section 8.3.1](#))
- Grade 3 or greater colitis

- Grade 3 or greater noninfectious pneumonitis irrespective of duration
- Grade 2 pneumonitis that does not resolve to  $\leq$  Grade 1 within 3 days of the initiation of maximal supportive care
- Grade 3 irAE (excluding colitis or pneumonitis) that:
  - does not downgrade to Grade 2 within 3 days after onset of the event despite optimal medical management including systemic corticosteroids, or
  - does not downgrade to  $\leq$  Grade 1 or baseline within 14 days
- Liver transaminase elevation  $> 8 \times$  ULN or total bilirubin  $> 5 \times$  ULN
- Grade 3 or greater non-irAE, except for the exclusions listed below:
  - Nausea, vomiting, anorexia, dehydration, or diarrhea that can be managed with typical medical interventions

The definition of DLT excludes the following conditions:

- Grade 3 fatigue lasting  $\leq 7$  days
- Grade 3 endocrine disorder (thyroid, pituitary, and/or adrenal insufficiency) that is managed with or without systemic corticosteroid therapy and/or hormone replacement therapy and the patient is asymptomatic
- Grade 3 inflammatory reaction attributed to a local antitumor response (e.g., inflammatory reaction at sites of metastatic disease, lymph nodes, etc)
- Concurrent vitiligo or alopecia of any grade
- Grade 3 infusion-related reaction (first occurrence and in the absence of steroid prophylaxis) that resolves within 6 hours with appropriate clinical management
- Grade 3 or 4 neutropenia that is not associated with fever or systemic infection that improves by at least 1 grade within 3 days. Grade 3 or Grade 4 febrile neutropenia will be a DLT regardless of duration or reversibility
- Grade 3 or 4 lymphopenia
- Grade 3 thrombocytopenia that is not associated with clinically significant bleeding that requires medical intervention, and improves by at least 1 grade within 3 days

- Isolated Grade 3 electrolyte abnormalities that are not associated with clinical signs or symptoms and are reversed with appropriate maximal medical intervention within 3 days

### **3.1.2 Dose Escalation Plan**

The first cohort of patients to be enrolled will begin with the mocetinostat 7-Day Lead-in Period, receiving 50 mg on 3 days (e.g., Monday, Wednesday and Friday) and will continue into the combination regimen, with 50 mg mocetinostat administered TIW and 1500 mg durvalumab administered Q4W.

For a patient within a dose cohort to be considered evaluable for the dose-escalation decision, the patient must have either been on study for one full cycle and have received treatment with durvalumab and at least 9 of 12 scheduled mocetinostat doses (75%) in Cycle 1 or have experienced a DLT in Cycle 1.

Decision making rules for cohort expansion and dose escalation or de-escalation based on the experience of patients treated at a dose level are presented in [Appendix 2](#).

To ensure sufficient patient experience at the dose selected as the RP2D, enrollment at any dose level under consideration may be expanded to include at least 6 patients.

### **3.1.3 Definition of Maximum Tolerated Dose**

The Maximum Tolerated Dose (MTD) is defined as the highest mocetinostat dose administered in the combination regimen associated with the decision to “stay with the current dose” as determined from the Dose-Finding Spreadsheet ([Appendix 2](#)) using the experience of at least 6 patients during the first 28-day treatment cycle.

### **3.1.4 Definition of Recommended Phase 2 Dose**

The RP2D will be the highest dose of mocetinostat evaluated that is associated with:

- sufficient safety/tolerability to anticipate that patients will typically be able to receive treatment with at least 75% of the intended dose intensity of mocetinostat and 100% dose intensity of durvalumab; and
- no observed  $\geq$ Grade 3 or serious irAEs causally related to the combination regimen.

A dose level below the MTD may be selected as the RP2D.

### **3.2 Phase 2**

The Phase 2 study will enroll patients with NSCLC into one of the following 4 population cohorts:

Cohort 1 – Patients naïve to treatment with immunotherapy, having tumor with no/low PD-L1 expression.

Cohort 2 – Patients naïve to treatment with immunotherapy, having tumor with high PD-L1 expression.

Cohort 3 – Patients previously treated with an anti-PD-L1 or anti-PD-1 agent with clinical benefit response followed by progression of disease.

Cohort 4 – Patients previously treated with an anti-PD-L1 or anti-PD-1 agent with progression or disease  $\leq$  16 weeks after initiation of treatment.

Tumor PD-L1 expression will be determined by the PD-L1 (SP263) CDx assay. No/low PD-L1 expression is defined as positivity  $< 25\%$  of tumor cells; high PD-L1 expression is defined as positivity  $\geq 25\%$  of tumor cells. Tumor samples used to establish PD-L1 expression for eligibility must have been collected after the most recent systemic therapy.

The sample sizes for the populations to be enrolled in the Phase 2 portion of the study are based on Predictive Probability Design, which allows for flexibility in the number of patients to be included at each stage in order to ensure that sufficient number of evaluable patients are available for decision to continue or to stop enrollment of additional patients.

- Cohorts 1, 3 and 4: Stage 1 of enrollment will include a minimum of 9 evaluable patients. With exactly 9 evaluable patients at Stage 1, if at least 1 patient has an Objective Response, 8 additional evaluable patients will be enrolled, for a total sample size of 17 evaluable patients. If at least 3 objective responses are observed, further investigation may be warranted.
- Cohort 2: Stage 1 of enrollment will include approximately 17 evaluable patients. With exactly 17 evaluable patients at Stage 1, if at least 5 patients have Objective Responses, 27 additional evaluable patients will be enrolled, for a total sample size of 44 evaluable patients. If at least 18 Objective Responses are observed, further investigation may be warranted.

The exact stopping rules for all cohorts will be calculated based on the Predictive Probability Design, once the exact number of patients evaluable at Stage 1 is known. The aim is to get a minimum of 9 evaluable patients at Stage 1 for cohorts 1, 3 and 4 and about 17 evaluable patients at Stage 1 for cohort 2.

The populations included in Cohorts 3 and 4, who have had progression of disease during treatment with a checkpoint inhibitor, represent a potential unmet medical need. For this reason, if results in Stage 2 of enrollment are of high interest, enrollment may be expanded to as many as 100 patients total in each cohort to narrow the 95% Confidence Interval (CI) around the ORR point estimate and more fully characterize the secondary endpoints in the population of interest.

In order to be part of the clinical activity evaluable population, the patient must have at least one on-study disease assessment or discontinue from treatment for PD prior to this assessment. Patients who discontinue treatment prior to the first on-study disease assessment for an AE, toxicity, or withdraw consent are considered non-evaluable for disease assessment. These patients will not be part of the clinical activity evaluable population.

Disease response and progression as documented by the investigator in the CRF will be the basis for patient management and study expansion decision making. Unconfirmed objective responses recorded in the CRF may be used as the initial basis for expansion of study enrollment; however, follow-up evaluations on patients with unconfirmed responses must continue to support the decision to continue to the full number of patients to be included in the next stage. Central radiology review for disease response and progression may be added to the study during Stage 2. If this occurs, central review of all radiologic assessments performed in the study will be expected (including retrospective review of patients enrolled in Stage 1), and central radiology review for disease response will be the basis for the primary statistical analyses to estimate the objective response rate and its confidence interval, as well as the duration of response and PFS.

Study treatment will continue until disease progression, unacceptable adverse events, patient refusal or death.

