#### **Statistical Design Applied to Phase 2 Cohorts 1, 3 and 4**

The ORR using a PD-L1 inhibitor in the population with advanced NSCLC having no or low PD-L1 expression, or prior disease progression on a checkpoint inhibitor, is assumed to be 5% ( $p_0$ ); thus this rate is considered uninteresting. The target ORR using mocetinostat in combination with durvalumab in this study is 30% ( $p_1$ ). Stage 1 of enrollment will include a minimum of 9 evaluable patients. With exactly 9 evaluable patients at Stage 1, if at least 1 patient has an Objective Response, 8 additional evaluable patients will be enrolled, for a total sample size of 17 evaluable patients. If at least 3 Objective Responses are observed, further investigation may be warranted. If the true ORR is 5% (null hypothesis), the probability of early termination during the study is 0.63; the Type 1 error is equal to 0.0466 and the power is equal to 0.9045.

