#### **Statistical Design Applied to Phase 2 Cohort 2**

The ORR using a PD-L1 inhibitor in the population with advanced NSCLC having high PD-L1 expression is assumed to be 27% ( $p_0$ ); thus this rate is considered uninteresting. The target ORR using mocetinostat in combination with durvalumab in this study is 50% ( $p_1$ ). Stage 1 of enrollment will include approximately 17 evaluable patients. With exactly 17 evaluable patients at Stage 1, if at least 5 patients have Objective Responses, 27 additional evaluable patients will be enrolled, for a total sample size of 44 evaluable patients. If at least 18 Objective Responses are observed, further investigation may be warranted. If the true ORR is 27% (null hypothesis), the probability of early termination during the study is 0.50; the Type 1 error is equal to 0.0303 and the power is equal to 0.9018.

The exact stopping rules for all cohorts will be calculated based on the Predictive Probability Design, once the exact number of patients evaluable at Stage 1 is known. The aim is to get about 9 evaluable patients at Stage 1 for cohorts 1, 3 and 4 and about 17 evaluable patients at Stage 1 for cohort 2.

If Stage 2 results in Cohorts 3 and 4 are of high interest for efficacy, enrollment may be expanded to as many as 100 patients total in each cohort to narrow the 95% Confidence Interval (CI) around the ORR point estimate. Table 14 presents estimates of the 95% CI around the observed ORR for several potential outcomes using the sample size of 100 patients, and the Clopper-Pearson method.

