The ORR using a PD-L1 inhibitor in the population with advanced NSCLC having high PD-L1 expression is assumed to be 27% (p_0); thus this rate is considered uninteresting. The target ORR using mocetinostat in combination with durvalumab in this study is 50% (p_1). Stage 1 of enrollment will include approximately 17 evaluable patients. With exactly 17 evaluable patients at Stage 1, if at least 5 patients have Objective Responses, 27 additional evaluable patients will be enrolled, for a total sample size of 44 evaluable patients. If at least 18 Objective Responses are observed, further investigation may be warranted. If the true ORR is 27% (null hypothesis), the probability of early termination during the study is 0.50; the Type 1 error is equal to 0.0303 and the power is equal to 0.9018.

The exact stopping rules for all cohorts will be calculated based on the Predictive Probability Design, once the exact number of patients evaluable at Stage 1 is known. The aim is to get about 9 evaluable patients at Stage 1 for cohorts 1, 3 and 4 and about 17 evaluable patients at Stage 1 for cohort 2.

If Stage 2 results in Cohorts 3 and 4 are of high interest for efficacy (as decided by the sponsor), enrollment may be expanded to as many as 100 patients total in each cohort to narrow the 95% Confidence Interval (CI) around the ORR point estimate.

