12.5 Efficacy Analyses

12.5.1 ORR, Best Overall Response and CBR

Descriptive statistics (frequency and percentage) for ORR, CBR and of best overall response (CR, PR, SD, PD) based on the Response Assessments by the Investigator and the exact 95% Clopper-Pearson confidence interval (SAS® PROC FREQ) of the response rate will be presented by phase and by dose level/cohort and overall within each phase. An exact test (SAS® PROC FREQ) for single proportion (two-sided $\alpha=5\%$) will be performed to test H_0 : ORR $\leq 5\%$ against H_1 : ORR $> 5\%$ in cohorts 1, 3, and 4 and to test H_0 : ORR $\leq 27\%$ against H_1 : ORR $> 27\%$ in cohort 2, for phase 2 of the study. Patients who cannot be assessed for response will be counted as non-responders. Descriptive statistics (frequency and percentage) for CR and PR rate will be presented by phase, dose level/cohort, and overall within each phase. In addition, exact binomial 95% CIs for the percentage will be displayed for CR and PR rate, respectively.

The primary analyses will be conducted in the clinical activity evaluable population. Supportive analyses will be presented in the mITT population.

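### If Cohort 3 or 4 is expanded on favourable Stage 2 results, the pooled ORR is biased upward, and its exact interval can fall below 95% coverage when the true ORR is low or the unstated trigger is strict

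*Protocol*

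**What the plan says.** Cohorts 1, 3 and 4 share a two-stage design with an uninteresting ORR of 5% and a target of 30% (Protocol 9.1.2; SAP 6.3.3). Stage 1 has 9 evaluable patients: "if at least 1 patient has an Objective Response, 8 additional evaluable patients will be enrolled, for a total sample size of 17 evaluable patients". The rule at 17 is "If at least 3 Objective Responses are observed, further investigation may be warranted".

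Cohorts 3 and 4 alone have a further step. Protocol 3.2 states that "if results in Stage 2 of enrollment are of high interest, enrollment may be expanded to as many as 100 patients total" per cohort, to narrow the 95% interval around the ORR and to describe the secondary endpoints more fully. SAP 6.3.4 adds that the condition is met when Stage 2 results "are of high interest for efficacy (as decided by the sponsor"). Neither document gives a response count for this decision.

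Protocol Table 14 gives intervals "for several potential outcomes using the sample size of 100 patients, and the Clopper-Pearson method". SAP 12.5.1 plans the "exact 95% Clopper-Pearson confidence interval" and an exact test against 5%, with the clinical activity evaluable population as primary. It does not separate patients enrolled before and after the expansion decision, and it names no adjusted estimator. Protocol 9.7 plans no interim analysis. SAP 10.0 describes only the look after the first stage.

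**The concern.** A cohort reaches 100 patients only because its first 17 did well. Among expanded cohorts those 17 therefore have a response rate selected to be high, and they make up at least 17% of the pooled denominator. An ordinary proportion and a fixed-n exact interval take no account of this.

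Narrowing the interval around the ORR is one of the two stated reasons for expanding, so the expanded-cohort ORR will be read as the main result. An upward shift would matter most when true activity is modest. Because the trigger is not stated, nobody can work out afterwards how large the shift was.

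**Working it through.** **Inputs.** True ORR p from 5% (null) to 30% (target); at least 1 of 9, then 8 more patients; at least 3 of 17 as the only numerical rule at that point (Protocol 9.1.2); a maximum of 100, hence 100 − 17 = 83 later patients. The high-interest trigger T is not given. I take T = 3 to 6 of 17 as an assumed range; only T = 3 appears in the documents for these cohorts.

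**Reproducing the plan.** Summing Bin(9, p)(x) × P(Bin(8, p) ≥ 3 − x) over x ≥ 1 gives 0.0466 at p = 5% and 0.9045 at p = 30%. The probability of stopping at 9 under the null is 0.95^9 = 0.630. All three match Protocol 9.1.2. The five intervals in Table 14 also reproduce, as ordinary fixed-n intervals for 100 patients.

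**Bias given expansion.** The later patients are unselected, so for a final size N

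bias = (17/N) × (mean rate in the first 17 given expansion − p).

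- T = 3, p = 10%: the first 17 average 20.5%; 0.17 × 10.5 = 1.8 points.
- T = 3, p = 30%: the first 17 average 31.9%; 0.17 × 1.9 = 0.3 points.
- T = 5, p = 10%: the first 17 average 30.9%; 0.17 × 20.9 = 3.6 points.

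**Coverage given expansion.** Exact enumeration of the 9 + 8 + 83 patients, keeping paths with at least 1 of 9 and at least T of 17, gives the probability that the n = 100 Clopper-Pearson interval contains p:

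| True ORR | Coverage, n fixed at 100 | T = 3: P(expand) | Bias (points) | Coverage | T = 5 (assumed): P(expand) | Bias (points) | Coverage |
|---|---|---|---|---|---|---|---|
| 5% | 0.983 | 0.047 | 2.4 | 0.929 | 0.001 | 4.3 | 0.746 |
| 10% | 0.956 | 0.223 | 1.8 | 0.944 | 0.022 | 3.6 | 0.855 |
| 15% | 0.966 | 0.456 | 1.3 | 0.959 | 0.098 | 2.9 | 0.913 |
| 20% | 0.967 | 0.663 | 0.9 | 0.968 | 0.240 | 2.3 | 0.947 |
| 30% | 0.963 | 0.905 | 0.3 | 0.965 | 0.609 | 1.2 | 0.963 |

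At p = 30% with T = 6 the bias is 1.9 points and coverage 0.956.

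**Direction of the misses.** They are almost all on the optimistic side. At p = 10% the lower limit lies above the truth in 5.5% of expanded cohorts with T = 3 and 14.5% with T = 5, against a nominal 2.5%.

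**Smaller expansion.** The factor 17/N grows as N falls. At p = 15% and T = 5 the bias is 2.88 points at N = 100 and 2.88 × 100/50 = 5.8 points at N = 50.

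**All paths.** Counting cohorts that stop at 9 or 17 as well, coverage is 0.960 to 0.999 and the mean ORR is biased downward, by 1.5 to 4.5 points.

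**Post-decision patients alone.** With 83 patients the ORR is unbiased given expansion, and exact coverage is 0.963, 0.975, 0.970, 0.961 and 0.959 at p = 5%, 10%, 15%, 20% and 30%.

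**The case against.** A reader might infer that the planned interval under-covers in general. The documents do not support that. Under the only numerical rule they contain, conditional coverage is below 95% only at 5% and, marginally, at 10%. The larger shortfalls rest on a trigger such as 5 of 17, which neither document states for these cohorts. They are also rare: at a true ORR of 10% with T = 5, expansion has probability 0.022, so expansion together with a falsely high lower limit has probability 0.022 × 0.145 = 0.003. Where expansion is likely the bias is small: 0.3 points at 30% with T = 3, against a half-width of about 9 points in Table 14. All of this stands.

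A reader might also infer that the pooled estimate should give way to the later patients alone. That is a trade-off. Under T = 3 the pooled estimate has the smaller conditional root mean square error at a true ORR of 15% and above (3.64 against 3.92 points at 15%).

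The all-paths result does not dispose of the point. It averages over cohorts that stopped early, whereas an ORR out of 100 exists only after expansion, and its reader needs its properties given expansion. The trigger may also be stricter than 3 of 17, because that count already carries its own consequence in the plan.

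**Conclusion.** The point holds in a limited form. Given expansion, the pooled ORR is biased upward at every true rate and trigger examined: by 0.3 to 2.4 points if the trigger is 3 of 17 and the expansion reaches 100, and by more with a stricter trigger or a smaller expansion. The exact interval can fall below 95% conditional coverage when the true ORR is low or the trigger is strict. At the 30% target it stays at or above 0.956 for triggers up to 6 of 17.

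The figures assume exactly 9 + 8 evaluable patients, full expansion to 100, and the same response definition and population for trigger and analysis. The documents leave room for differences. Unconfirmed investigator responses may start an expansion while ORR counts confirmed ones. Central review may become the basis of the primary ORR. Protocol 9.3.1 uses the mITT population for the decision to go to 100, while SAP 12.5.1 makes the evaluable population primary. Any of these would change the size of the bias. The basic gap is the missing threshold, without which the size cannot be fixed.

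**What to change.** In SAP 6.3.4, state before the Stage 2 look the number of responses that counts as high interest, with the response definition and population used, and record the count when the decision is taken.

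In SAP 12.5.1, for any cohort expanded beyond Stage 2, report the ORR and exact 95% interval in patients enrolled after the decision beside the pooled result, and label the pooled estimate as conditional on a favourable Stage 2. Once a threshold is stated, an estimator conditional on crossing it may replace the post-decision estimate. Conditioning on the exact trigger count would gain nothing, since it reduces to the post-decision analysis.

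The cost is one extra table row and no extra patients. The post-decision interval is about 10% wider at 83 patients: 21/83 gives 16.4-36.0% (width 19.6 points) against 16.9-34.7% for 25/100 (width 17.8 points), a ratio of 1.10. It is wider still if fewer than 83 are added. The SAP provides for a final version before database lock, so the reporting change fits its own process; the threshold has to be set earlier, before the Stage 2 results are seen.
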